3.1.2. Secondary Analyses

For safety, the incidence of device-related adverse events/incidents will be assessed up to 10 years after the index procedure and monitored through collection and analyses.

Furthermore, time to (earliest) Device-Related Adverse Events will be analyzed as well. For analysis of the time to the (earliest) Device-Related Adverse Events, the Kaplan-Meier method will be used. Considered variables, the level of measurement and the planned analysis steps are listed in detail in the SAP. These analyses will be part of the final report.

3.1.3. Additional Analyses

Additional Analyses are outlined in the subsequent sections. Analysis details (variables, level of measurement, planned steps) are listed in-depth in the SAP.

- **Mortality**

For analysis of the time to death or mortality, the Kaplan-Meier method will be used. The times between surgery and the last available assessment will be used together with the times between date of surgery and the date of death. This analysis will be part of the final report.

- **ASES Total Score – Within subject changes by visit**

[figure not shown]
The within subject score changes of the ASES Total Score from visit to visit will be analyzed to help identify the changes on the subject level. This analysis will be part of the final report.

3.2. SAMPLE SIZE

The determination of sample size is based on benchmark sources and values. To account for an estimated appropriate overall drop-out rate, Stryker intends to enroll the calculated number of subjects, multiplied

[figure not shown]
by the number of cleared indications to reflect the underlying subject population adequately. For details, please see Table 3.2.

Benchmark and Objectives for Clinical Investigation					
Endpoint		Non-inferiority (equal or better) of the ASES Shoulder Score in relationship to the officially cleared indications in comparison to respective clinical outcome data in the scientific literature.			
Estimated drop-out rate		56% (confirmed by Medical Expert, see Cuff et al.) Cuff et al. Reverse Shoulder Arthroplasty for the Treatment of Rotator Cuff Deficiency: A Concise Follow-up, at a Minimum of 10 Years, of Previous Reports. J Bone Joint Surg Am. 2017 Nov 15;99(22):1895-1899. doi: 10.2106/JBJS.17.00175.			
Benchmark Sources & Values ASES [points]					
Source		n	Mean	Std. Dev.	Comments No.
No.	Title				
1	Irlenbusch et al. [10]	73	77.9	N/A	Conflict related to Follow-Up times in abstract vs method vs result section.
2	Flurin et al. [20]	73	90.3	14.6	Not clear if SD or 95% CI
3	Press et al. [22]	34	82.6	19.4	
4	Hsu et al. [23]	25	94.4	N/A	
5	Kiet et al. [26]	40	80	21	N changed from 45 to 40
6	Steen et al. [29]	96	80.4	22.4	Not clear if SD or 95% CI
7	Gulotta et al. [34]	40	80.1	10.1	
8	Petri et al. [49]	43	83.5	13.1	
9	Schoch et al. [62]	78	88.4	16.7	
10	Alentorn-Geli et al. [70]	38	64	N/A	TSA und HA combined.
Identified Cleared Indications					
No.	Indication				
1	Post-traumatic arthritis				
2	Degenerative arthritis				
3	Rheumatoid arthritis				
4	Revision of previously failed shoulder joint replacement				
5	Aseptic necrosis				
Explorative Meta-Analysis - ASES (single group)					
Acceptance Criteria					
Confidence Interval (CI)					0.95 (95%) two-sided
Software Used					IBM SPSS V20
Case Processing Summary					
		Cases			
		Valid		Missing	
		N	Percent	N	Percent
Mean ASES ReUnion_TSA_CER		10	100,0%	0	0,0%
Std.Dev. ASES ReUnion_TSA_CER		7	70,0%	3	30,0%
				10	100,0%

Descriptives								
			Statistic					
Std.Dev. ASES ReUnion_TSA_CER	Mean	16,7571						
	95% Confidence Interval for Mean	Lower Bound	12,6353					
		Upper Bound	20,8790					
	Median	16,7000						
	Std. Deviation	4,45678						
	Minimum	10,10						
	Maximum	22,40						
	Interquartile Range	7,90						
Mean ASES ReUnion_TSA_CER	Mean	82,1600						
	95% Confidence Interval for Mean	Lower Bound	76,2372					
		Upper Bound	88,0828					
	Median	81,5000						
	Std. Deviation	8,27945						
	Minimum	64,00						
	Maximum	94,40						
	Interquartile Range	9,40						
								
Red line: Pooled mean ASES Blue lines: 95% CI of pooled mean ASES Black line: Pooled median pooled ASES Box: Interquartile Range Green Line: Pooled mean ASES minus pooled std. dev. ASES (16.76) $82.16 - 16.76 = \mathbf{65.40 \text{ points}}$								
Acceptance Criteria for Sample Size Calculation								
Significance Level (α)	0.05 (5%)							
Power (1- β)	0.80 (80%)							
Confidence Interval (CI)	0.95 (95%)							
Tails	2							
Path	Non-inferiority – ReUnion TSA (A) \geq Benchmark (B, explorative meta-analysis in this document)							
Hypotheses Pair	Null (H_0)	$A - B < -\theta$						
	Alternative (H_1)	$A - B \geq -\theta$						
Benchmark Timepoint	24 months postoperative							
Benchmark n (sources)	10							
Benchmark Mean	82.16 (pooled mean ASES [points])							
Benchmark Std. Dev.	16.76 (pooled std. dev. ASES [points])							
Benchmark Value Non-Inferiority Margin (- θ)	Pooled mean ASES minus pooled std. dev. ASES (16.76) $82.16 - 16.76 = \mathbf{65.40 \text{ points}}$							
Software Used	IBM SPSS Sample Power V3.0							
IBM SPSS Sample Power Output								
One goal of the proposed clinical investigation is to test the null hypothesis that the population mean is 82.16 points. The criterion for significance (alpha) has been set at 0.05. The test is 2-tailed, which means that effects in both directions will be interpreted. With the proposed sample size of 10 cases, the clinical investigation will have power of 80.3% to yield a statistically significant result. This computation assumes								

that the population from which the sample will be drawn has a mean of 82.16 points with a standard deviation of 16.76 points. The observed value will be tested against a theoretical value (constant, non-inferiority margin) of 65.40 points.

IBM SPSS Sample Power Output – Screenshot

Estimated overall drop-out rate is 56% which leads to the requirement of enrolling additional 6 subjects into the clinical investigation.

Sample Size	Number of subjects to be enrolled: 16 subjects (rounded up to 20 subjects)
Overall Sample Size (multiplied by number of indications (=5)	100 subjects

Table 3.2: Sample Size Justification

In conclusion, the calculated number of subjects to be enrolled (10), plus the estimated overall drop-out rate of 56%, leads Stryker's enroll 20 subjects per cleared indication (5) to reflect the underlying subject population adequately. As a result, an enrollment target of 100 subjects in total will be aspired (ideally, but not necessarily, composed with 20 subjects per indication).

4. Methods

4.1. RANDOMIZATION

No specific methods for assigning subjects will be used for this clinical investigation. A consecutive series of subjects at each site meeting all the eligibility criteria will be enrolled in this clinical investigation.

4.2. STATISTICAL INTERIM ANALYSES AND STOPPING GUIDANCE

Interim analyses will be performed on a yearly basis. The progress of the clinical investigation will be reported together with the interim results on the variable level according to the analysis plan.

The analysis of the primary endpoint / objective will be part of the related interim / annual report when all subjects have completed the 24 months postoperative including the ASES Shoulder Score.

There will be no stopping rules specified for this clinical investigation.

4.3. TIMING OF FINAL ANALYSES

The full final report with complete analysis, progress and conduct reporting will be created at the end of this clinical investigation.

4.4. TIMING OF OUTCOME ASSESSMENT

Subjects in this clinical investigation will be evaluated at Pre-Operative, Operative/Discharge, and at 6 Weeks (4 weeks – 8 weeks), 6 Months (24 weeks – 28 weeks), 12 Months (48 weeks- 56 weeks), 24

Months (100 weeks – 108 weeks) and annually after the index procedure. The follow-up evaluations will include assessment of device-related AEs/incidents, radiographs and ASES Shoulder Score.

Assessment	Preoperative	Operative/ Discharge	6 Weeks ^{a, b} (+/- 2 weeks)	6 Months ^{a, b} (+/- 3 weeks)	12 Months ^{a, b} (+/- 4 weeks)	24 Months ^{a, b} (+/- 4 weeks)	Annually ^b
Informed Consent	X						
Demographics & Medical History	X						
Inclusion/Exclusion	X						
Physical Exam	X		X ^c	X ^c	X ^c	X ^c	X ^c
Surgical Procedure		X					
ASES Shoulder Score	X		X ^d	X ^d	X ^d	X ^d	X ^d
Image Evaluation ^{e, f}	X	X	X	X	X	X	X
Subject Disposition ^g			X	X	X	X	X
	Device-Related AEs/Incidents & Reoperations will be collected throughout the course of the clinical investigation.						
	
 a. Follow-up visit schedule to reflect Institutions' Standard of Care practices b. If the subject misses a visit and is outside of the visit window, then every effort should be made to collect data instead of noting visit as missed. c. Evaluation may be collected when subject presents in-clinic for study visit. d. Evaluation can be collected via phone. e. Radiograph collection should follow Institution's Standard of Care practices and no additional x-rays should be made for study purposes. f. CT scans may be collected if part of Institution's Standard of Care practices. g. Subject Disposition assessment will occur at any time point for subject withdrawal prior to the completion of the clinical investigation. 						

Table 4.4: Schedule of Events

4.5. STATISTICAL SOFTWARE

Statistical Analysis will be performed using IBM SPSS, IBM SPSS Sample Power as well as established standard software packages (e.g. MS Excel).

4.6. MISSING DATA

The intent is to collect as complete a dataset as possible. Nevertheless, in some situations missing data cannot be avoided. The reports and tables therefore will show the number and percentage of missing cases for each analyzed variable in relation to the enrolled cases for each postoperative assessment

Any deviations from Statistical Analysis Plan will be listed in the annual or final reports.

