9.3. WITHDRAWAL CRITERIA

If during the clinical investigation a subject must be withdrawn prematurely, then the procedures outlined in this section must be followed. These procedures should not interfere with the initiation of any new treatments that are necessary to treat a subject's condition. Information on all withdrawn subjects will be documented.

Subjects may be withdrawn from the clinical investigation for any of the following reasons:

- i. Subject Withdrawal: A subject may voluntarily withdraw from the clinical investigation at any time and for any reason. The subject should be asked when possible, and without any form of coercion, the reason for his/her decision. If the participant withdraws from the clinical investigation completely, then data collected up until the point of withdrawal will be included in the final analysis.
- ii. Lost to Follow-Up (LTFU): A subject will be considered LTFU after all reasonable efforts have been made to contact the subject and request his/her continued participation in the clinical investigation. All attempts to contact the subject must be documented and should include at least two attempts to contact the subject by phone and one attempt via a certified letter. Data collected up until the point where the subject is LTFU will be included in the final analysis.
- iii. Removal of Device or AE/Incident: The discontinuation of a subject's participation in the clinical investigation due to the removal of the ReUnion TSA System or AE/incident that prohibits his/her continued participation must be fully explained. All available information concerning the removal of the device or AE/incident should be provided. Data collected up until the point of removal or AE/incident will be included in the final analysis.
- iv. Death: The discontinuation of a subject's participation in the clinical investigation due to death must be fully explained. All available information concerning the death or AE should be provided. Removal of a subject from continued follow-up in the clinical investigation due to death will not be considered a device failure unless the death is

directly caused by, or attributable to, the ReUnion TSA System. Data collected up until the point of death will be included in the final analysis.

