11.3.2. Primary Analysis / Endpoint

The objective of the clinical investigation is to demonstrate non-inferiority (equal or better) of the ASES Shoulder Score in relationship to the officially cleared indications in comparison to respective clinical outcome data in the scientific literature.

[figure not shown]
Data collection of ASES Shoulder Score will start pre-operatively and will be collected according to schedule in Table 1. This will be repeated annually in all subjects who have the total or partial prosthesis with full or partial implant survival (including all subjects without removal of all endo-prosthesis components).

The 24 months post-operative results for subjects implanted with ReUnion TSA System will be compared to a historical group and results reported by respective clinical outcome data in the scientific literature. The benchmark sources and values will serve as the control group for the ReUnion TSA System subjects.

Higher ASES Shoulder Score results are linked to better subject results and vice versa.

The clinical investigation endpoint is non-inferiority to the control, meaning the clinical investigation result should be equal or better than the control. In this clinical investigation, an equal or better ASES Shoulder Score result means equal or more (\geq). As only results from samples will be captured, results are mostly estimates of the true population parameter. These estimates vary by a certain area, where it is expected that the true population parameter falls within. Based on this, it is required to specify a lower limit for the acceptable difference or zone of indifference, denoted as $-\theta$.

Hypotheses are developed to allow for a comparison of the 24 months post-operative ASES Shoulder Score effectiveness / performance between the two underlying populations. The 24 months post-operative ASES Shoulder Score is the primary endpoint of this clinical investigation. Hypothesis tests will be one-sided with a significance level α of 5%.

Hypothesis	Equations	Interpretation
Null (H_0)	$A - B < -\theta$	Central tendency of A is inferior to the central tendency of B.
	ReUnion TSA System – Control (Benchmark) $< -\theta$	
Alternative (H_1)	$A - B \geq -\theta$	Central tendency of A is non-inferior to the central tendency of B.
	ReUnion TSA System – Control (Benchmark) $\geq -\theta$	
		
Possible Evidence (p)	Possible Decisions	Possible Conclusions – ASES score

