3.1.1. Primary Analysis / Endpoint

The objective of the clinical investigation is to demonstrate non-inferiority (equal or better) of the ASES Shoulder Score in relationship to the officially cleared indications in comparison to respective clinical outcome data in the scientific literature.

[figure not shown]
Data collection of ASES Shoulder Score will start pre-operatively and will be collected according to schedule in Table 4.4. This will be repeated annually in all subjects who have the total or partial prosthesis with full or partial implant survival (including all subjects without removal of all endo-prosthesis components).

The 24 months postoperative results for subjects implanted with ReUnion TSA System will be compared to a historical group and results reported by respective clinical outcome data in the scientific literature. The benchmark sources and values will serve as the control group for the ReUnion TSA System subjects.

Higher ASES Shoulder Score results are linked to better subject results and vice versa.

The clinical investigation endpoint is non-inferiority to the control, meaning the clinical investigation result should be equal or better than the control. In this clinical investigation, an equal or better ASES Shoulder Score result means equal or more (\geq). As only results from samples will be captured, results mostly are estimates of the true population parameter. These estimates vary by a certain area, where it is expected that the true population parameter falls within. Based on this, it is required to specify a lower limit for the acceptable difference or zone of indifference, denoted as $-\theta$.

Hypotheses were developed to allow for a comparison of the 24 months postoperative ASES Shoulder Score effectiveness / performance between the two underlying populations. The 24 months postoperative ASES Shoulder Score is the primary endpoint of this clinical investigation. Hypothesis tests will be one-sided with a significance level α of 5%.

Hypothesis	Equations	Interpretation
Null (H0)	$A - B < -\theta$	Central tendency of A is inferior to the central tendency of B.
	ReUnion TSA System – Control (Benchmark) $< -\theta$	
Alternative (H1)	$A - B \geq -\theta$	Central tendency of A is non-inferior to the central tendency of B.
	ReUnion TSA System – Control (Benchmark) $\geq -\theta$	
		
Possible Evidence (p)	Possible Decisions	Possible Conclusions – ASES Shoulder Score

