6.6. ANALYSIS OF CI ENDPOINTS

Evaluation Variable / Question	Level of Measurement	Analysis Plan					
Endpoints – Primary Endpoint							

Use variable Total ASES Shoulder Score 24 Months [points]: Based on the underlying distribution of the data and the result of the normality assessment, either the parametric one-sample t-test or the non-parametric one-sample sign test will be used to compare the 24 months postoperative ASES Shoulder Score results of the ReUnion TSA group against the lower maximum acceptable difference ($-\theta$) of 65.40 points.
 
The analysis of the primary endpoint will be part of the final report.
							

Table 6.6.1: Endpoints – Primary Endpoint Tables List

Evaluation Variable / Question	Level of Measurement	Recode and Analysis Plan	Inclusion		
Adverse Events – Time to (earliest) Device-Related Adverse Event / Incident			IR	FR	N/A
Creation of variable Difference between Date of Surgery [dd.mm.yyyy] and Date of First Device Related Adverse Event [dd.mm.yyyy] in days / (Variable(s): VISITDT; AEONSTDT)	Quantitative, ratio	Case summary with number and percentage of valid cases/values, missing cases/values (if any) and total cases/values. Mean, median, interquartile range, maximum, minimum, standard deviation, 95% confidence interval for mean, Shapiro-Wilk Test.		X	
Creation of variable Difference between Date of Surgery [dd.mm.yyyy] and Date of “most recent” Visit [dd.mm.yyyy] in days / (Variable(s): VISITDT)	Quantitative, ratio	N/A (Analyzed above), used for survivorship		X	

Create new variable “Grouping variable – First Device Related Adverse Event” (Variable(s): AEONSTDT)	Qualitative, nominal	- censored = survivors - events = first (earliest) Device Related Adverse Event		X	
Create new variable “Combined Time – First Device Related Adverse Event” (Variable(s): AEONSTDT)	Quantitative, ratio	- Use time between surgery and “most recent” visit for surviving subjects - Use time between surgery and first device related adverse event for subjects with device related adverse event		X	

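### The primary 24-month ASES test has no missing-data method and no rule for complete implant removals, so it is an observed-case analysis that may favour success

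*SAP*

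**What the plan says.** - **Missing data.** SAP 4.6: "The reports and tables therefore will show the number and percentage of missing cases for each analyzed variable", relative to the enrolled cases. Protocol 11.4 says the same. Neither document names an imputation method, a missingness assumption or a sensitivity analysis.
- **Primary test.** SAP 6.6 takes the 24-month total ASES score and says that "either the parametric one-sample t-test or the non-parametric one-sample sign test will be used" to compare it with 65.40 points. SAP 3.1.1 and Protocol 11.3.2 agree.
- **Who keeps being scored.** Under Protocol 11.3.2 and SAP 3.1.1, ASES is repeated annually "in all subjects who have the total or partial prosthesis with full or partial implant survival". A parenthesis adds that anyone who has not lost every component still counts.
- **Withdrawal.** Protocol 9.3 lists device removal among the reasons for which a subject may be withdrawn, and adds: "Data collected up until the point of removal or AE/incident will be included in the final analysis".
- **Expected loss.** SAP 3.2: "Estimated overall drop-out rate is 56% which leads to the requirement of enrolling additional 6 subjects into the clinical investigation". The rate is cited to a report whose title gives a minimum follow-up of 10 years. No separate 24-month rate appears.
- **Analysis sets.** If any subject is excluded from the per-protocol set, an intent-to-treat set of all enrolled subjects is also analysed, in the final report only (Protocol 11.2, SAP 5.1). It has no rule for a missing score.

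**The concern.** A one-sample test at a single visit can use only the scores observed at that visit. The protocol keeps data collected before withdrawal, but nothing says how those data would supply a 24-month value, so for the primary test the promise has no effect. A subject whose whole implant is removed before 24 months may have no score at all, and that is the outcome least favourable to the device.

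If subjects who are removed, withdrawn or lost do worse than those who are scored, the observed mean overstates the mean of everyone implanted, in the direction of declaring non-inferiority. The study is single-arm and unblinded, so no concurrent control group shares the same loss and offsets it.

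**Working it through.** **Inputs from the documents:** assumed mean 82.16, SD 16.76, test value 65.40, base n = 10, stated power 80.3%, overall drop-out 56%, enrolment 100. **Assumed here:** 20% (also 5% and 10%) missing as lower alternatives, a scored mean of 72, and the gaps between scored and unscored subjects.

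**1. The plan's own figure.** With (82.16 − 65.40)/16.76 = 1 SD, n = 10 and two-sided α = 0.05, the noncentral t distribution gives power of 80.31%, matching the stated 80.3%.

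**2. Is power the problem?** No. At 56% loss, 100 × 0.44 = 44 subjects are scored, and power at the assumed mean exceeds 99.9%. The exposure is bias.

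**3. Bias.** Let f be the missing share, C the mean of scored subjects and M the mean of unscored subjects.

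- Whole-cohort mean = (1 − f)C + fM
- Overstatement = C − whole-cohort mean = f(C − M)

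For a 10-point gap this is 0.56 × 10 = 5.6 points at 56% missing, and 0.20 × 10 = 2.0 points at 20%. With no gap it is zero.

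**4. Tipping gap.** Setting the whole-cohort mean to 65.40 gives C − M = (C − 65.40)/f.

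| Mean of scored subjects | 56% missing | 20% missing (assumed) |
|---|---|---|
| 82.16 (plan's assumption) | 16.76/0.56 = 29.9 | 16.76/0.20 = 83.8 |
| 72 (assumed) | 6.60/0.56 = 11.8 | 6.60/0.20 = 33 |

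The 83.8-point gap would need the unscored subjects to average 82.16 − 83.8 = −1.6, which is impossible. The 29.9-point gap would need them to average 52.2.

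**5. At the pass mark.** With 44 scored, SD 16.76 and one-sided α = 0.05, an observed mean of about 69.65 passes. There the tipping gap is only (69.65 − 65.40)/0.56 = 7.6 points.

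**6. Effect on the error rate.** Suppose the whole-cohort mean is exactly 65.40, SD is 16.76 among those scored, 100 are enrolled, and unscored subjects average 10 points lower (assumed). The one-sided 5% t-test then declares success with these probabilities:

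| Missing | Scored | Bias (points) | P(success) |
|---|---|---|---|
| 5% | 95 | 0.5 | 9% |
| 10% | 90 | 1.0 | 14% |
| 20% | 80 | 2.0 | 28% |
| 56% | 44 | 5.6 | 70% |

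With no gap it stays at 5% throughout. For complete removals alone, an assumed 5% removed with a 30-point deficit gives a bias of 0.05 × 30 = 1.5 points and a false-success probability of 22%.

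**The case against.** The case on the other side has real force.

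- **The 56% figure.** A reader might infer that more than half the 24-month scores are expected to be missing. The documents do not establish that: the rate is called overall, its source has at least 10 years' follow-up, and this study also runs to 10 years. It remains true that the plan applies 56% to a sample size for the 24-month endpoint and offers no other rate.
- **Removed implants.** A reader might infer that all failures leave the mean by rule. They do not. Partial removals and component revisions stay in. Withdrawal after removal is something that may happen, not something automatic. The survival condition is attached to the annual repeats, while the schedule lists 24 months as its own column, so exclusion at 24 months is one reading. Complete removals can drop out; the text does not settle whether they must. Reoperations are also reported separately, including by Kaplan-Meier (SAP 6.1 and 6.7.3).
- **Direction.** No scores for lost subjects are given. For ordinary loss to follow-up, a bias towards success is an inference. For complete removals, an upward effect is the natural expectation.
- **Earlier scores.** They are not wasted: SAP 6.5, 6.7.1 and 6.7.4 summarise and compare them by visit. They are unused only in the primary test.
- **Mitigation.** ASES by phone, collection outside the window, contact before visits, and two calls plus a certified letter before a subject counts as lost should all reduce missingness. None says how to analyse what remains.
- **Robustness.** If scored subjects reach 82.16 and loss is modest, the conclusion cannot be overturned. That stands, but the plan contains no analysis that would demonstrate it.

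**Conclusion.** The point holds in a limited form. As written, the primary analysis is an observed-case test with no missing-data method, no stated handling of complete removals before 24 months and no sensitivity analysis. It may favour success. The documents do not support saying that it does, or by how much, because both the 24-month missing share and the scores of unscored subjects are unknown.

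How much this matters depends on where the result falls. At the planned mean of 82.16, reversal needs a large gap even at 56% missing and is impossible at 20%. Near the pass mark, with heavy loss, a gap of under 8 points is enough. These figures rest on SD 16.76 and 100 enrolled subjects where a test is involved, and on the assumed missing shares and gaps. The change is worth making because it concerns the validity of the primary claim and uses data already scheduled for collection.

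**What to change.** Amend SAP 4.6 and 6.6, and Protocol 11.3.2 and 11.4 to match, before the 24-month scores are analysed:

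1. Make the primary estimate the 24-month mean for all implanted subjects, from a repeated-measures mixed model or multiple imputation that uses the pre-operative, 6-week, 6-month and 12-month ASES scores. Test it against 65.40.
2. State in advance how complete removals before 24 months enter the estimate, with an unfavourable value at least as a sensitivity analysis. The subject's own pre-operative score is one option among several. Any such choice also needs a comment on comparability, since the documents do not show how the literature benchmarks treated removals.
3. Add a delta-adjusted tipping-point analysis that reports how much lower the unobserved scores must be before the conclusion against 65.40 changes.
4. Keep the observed-case t-test or sign test as a sensitivity analysis.
5. State the missingness expected at 24 months, separately from the overall rate.

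The cost is SAP and protocol wording and some extra analysis, with no new visits or data. The price is reliance on a missing-at-random model for the main estimate, which item 3 then probes, and a slightly wider interval.
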